# 11. STUDY MATERIALS AND MANAGEMENT

#### 11.1 DESCRIPTION OF STUDY PRODUCT

Ovaprene™ is a new, prescription monthly method of birth control that combines a porous, soft mesh cervical barrier encircled by a silicone intravaginal ring that slowly releases non-hormonal ingredients that antagonize sperm motility and viability. The device is inserted at the end of menses, left in place over the course of one menstrual cycle, and removed at the start of menses. Ovaprene™ is designed as a single size device with a diameter of 55 mm, similar to FDA approved, hormone-containing 54 mm diameter NuvaRing® device, eliminating the need for a specifically sized fitting or insertion by a health care professional. Thus, Ovaprene™ is a single device designed to provide the features that contracepting women want: efficacy, ease of use, ease of adherence, low or no side effects and easy reversal.

Ovaprene™ was studied in a human clinical trial as a non-significant risk device published in 2009.¹ Prior to this study, Ovaprene™ underwent a series of *in vitro* and animal tests to determine usability and design parameters, and to assess its initial safety and contraceptive efficacy. These background data are considered proprietary, but major conclusions are summarized in this section, with additional detail published in Del Priore *et al.*¹

To determine the putative barrier properties of Ovaprene™, the effectiveness of the mesh component in blocking human sperm was tested in an *in vitro* environment having features similar to those of the human cervix. After 20 hours of continuous exposure to sperm, there was no evidence of sperm passage through the Ovaprene™ mesh. Burst testing, under forces two orders of magnitude higher than expected during normal use, confirmed that no delamination or slippage of the mesh component from the ring matrix is expected during placement, and up to 35 days of use.

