#### 14.2.3 Secondary Objective: Release of active component from device

The mean, median, SD, and IQR of ferrous gluconate values associated with fewer than 5 progressively motile sperm per HPF will be calculated across all women. The mean, median, SD, and IQR of ferrous gluconate values at each time point at which it is collected will also be calculated across all women. The mean, median, SD, and IQR of ferrous gluconate values in used devices will be calculated. The mean, median, SD, and IQR of cervical mucus and vaginal pH before and after sex in the absence of and the presence of the device will be calculated across all women.

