- d) The sample size, mean, median, and standard deviation for the average number (across 9 HPFs) of progressively motile sperm per HPF in cervical mucus, across all treated subjects, in the presence of the Ovaprene® device. This is similar to that in Bullet b), but will be done at Visit OP3A, and also at Visit OP3B, by sub-setting the CRF MU data at VISIT\_ID = 14, and at VISIT\_ID = 19, respectively.
- e) The change from Baseline for the average number (across 9 HPFs) of progressively motile sperm per HPF in cervical mucus, across all Ovaprene® subjects. The change from Visit BP2 to Visit OP3A will be calculated by the value of MUAVPMS at Visit OP3A the value of MUAVPMS at Visit BP2. Then this change will be summarized by the sample size, mean, and median, and standard deviation across all treated subjects. Similarly, the changes from Visit BP2 to Visit OP3B will be calculated by replacing the Visit OP3A with OP3B.
- f) Overall percent of cycles with fewer than 5 PMS in the presence of Ovaprene® device. The numerator for this percentage will be the sum of all Ovaprene® device use cycles in the above Bullet c), and the denominator will be the total number of cycles from all treated with Ovaprene® and with MUAVPMS values.
- g) The sample size, mean, median, and standard deviation for the average number (across 9 HPFs) of progressively motile sperm per HPF in cervical mucus, across all Ovaprene® device cycles. This is similar to that in Bullet d), but will be inclusive of Visit OP3A and Visit OP3B.

Note that if a PCT cycle met the following 2 criteria that made the cycle invalid for the analysis, that cycle will be excluded from the efficacy analysis, but all safety data in that cycle will still be included in safety analysis:

- There is No, or Insufficient, material for sperm present in the vaginal pool, and
- Sperm at 100x and 400x also equals 'No'.

The secondary efficacy analysis will focus on the release of active component from the device in vaginal and cervix samples, and consists of the following endpoints:

- a) Determine the concentration release curve of ferrous gluconate in cervicovaginal fluid (CVF) over the first 4-6 hours after Ovaprene® insertion at one clinical site
- b) Determine whether the minimum target level of 8.2  $\mu$ g/mL is achieved in the first 4-6 hours after Ovaprene® insertion at one clinical site.

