- c) Levels of ferrous gluconate in CVF before sex that are associated with fewer than 5 progressively motile sperm per HPF in the cervical mucus after sex (i.e. success), during ovulation. Summary statistics of sample size, mean, median, standard deviation, and IQR will be presented by visit.
- d) Levels of ferrous gluconate in CVF at multiple time points in the safety cycle in the absence of coitus. This will allow the estimation of how long after insertion it takes to reach the target concentration levels associated with success and whether target levels are still present up to 29 days after insertion. Summary statistics of sample size, mean, median, standard deviation, and IQR will be presented by visit and assessment timepoint.
- e) Levels of ferrous gluconate in CVF before and at multiple time points after sex at ovulation with the device in place. This will allow determination of whether they are different from before sex and, if so, how much time is needed to return to pre-sex levels at all visits in Ovaprene® PCT cycles in both vaginal and cervical fluid. Summary statistics of sample size, mean, median, standard deviation, and IQR will be presented by visit and assessment time-point.
- f) Vaginal pH (from Vaginal Sample CRF) and cervical pH (from Cervical Mucus CRF) before and after sex in the absence and presence of the device. Six-number summary for the observed values and difference between pre-sex and after sex will be presented by visit. For the study site (EVMS only) with multiple timepoints at a visit, the summary will be done at each timepoint. The average of pH values within each visit over the multiple timepoints will be calculated for each subject, and then be summarized. The goal of these assessments during the Ovaprene® safety cycle is to look at the effect of study device in the absence of sex.
- g) Residual amount of ferrous gluconate in Ovaprene® devices that have been worn over a cycle of use. Six-number summary statistics will be presented by visit and by duration of time the device was worn (1-7 days, 8-14 days, 15-21 days, 22-28 days and >28 days).
- h) Cervical mucus score. Summary statistics mean, median, standard deviation, and IQR will be presented by visit. The number and percent of subjects with cervical mucus score ≥ 10 in each Ovaprene cycle will also be presented. For the summary of cervical mucus score ≥ 10, cervical mucus data will only be used from the cycle that occurs after the highest OPK result for that cycle.

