| 14.2.1.1-Dis    | Number and Percent of Subjects with an Average of Fewer Than 5 Progressively Motile Sperm per HPF in Cervical Mucus by Subjects Had Ring Dislodgement or Not            | Ovaprene with at Least One PCT Cycle |
| 14.2.1.2        | Average Number (across 9 HPFs) of Progressively Motile Sperm per HPF in Cervical Mucus and Change from Baseline Cycle to Ovaprene PCT Cycles                            | Ovaprene with at Least One PCT Cycle |
| 14.2.1.3        | Number and Percent of Ovaprene Cycles with Fewer Than 5 PMS per HPF in Cervical Mucus   | Ovaprene with at Least One PCT Cycle |
| 14.2.1.4        | Number and Percent of Subjects with Fewer Than 5 PMS per HPF in Cervical Mucus  | Ovaprene with at Least One PCT Cycle |
| 14.2.2.1-E      | Summary of the Levels of Ferrous Gluconate in CVF at Study Site EVMS  | Ovaprene with at Least One PCT Cycle |
| 14.2.2.1-E-5PMS | Summary of the Levels of Ferrous Gluconate in CVF at Study Site EVMS for Subjects with Fewer Than 5 PMS per HPF in the Cervical Mucus after Sex                         | Ovaprene with at Least One PCT Cycle |
| 14.2.2.1-NE     | Summary of the Levels of Ferrous Gluconate in CVF at Non-EVMS Sites   | Ovaprene with at Least One PCT Cycle |

| Table Number         | Table Title  | Population                    |
|----------------------|--|--------------------------------------|
| 14.2.2.1-NE-
5PMS | Summary of the Levels of Ferrous Gluconate in CVF at Non-
EVMS Sites for Subjects with Fewer Than 5 PMS per HPF in the
Cervical Mucus after Sex    | Ovaprene with at Least One PCT Cycle |
| 14.2.2.2-E           | Summary of the Levels of Ferrous Gluconate in Cervix at Study Site EVMS  | Ovaprene with at Least One PCT Cycle |
| 14.2.2.2-E-5PMS      | Summary of the Levels of Ferrous Gluconate in Cervix at Study Site EVMS for Subjects with Fewer Than 5 PMS per HPF in the Cervical Mucus after Sex       | Ovaprene with at Least One PCT Cycle |
| 14.2.2.2-NE          | Summary of the Levels of Ferrous Gluconate in Cervix at Non-EVMS Sites   | Ovaprene with at Least One PCT Cycle |
| 14.2.2.2-NE-
5PMS | Summary of the Levels of Ferrous Gluconate in Cervix at Non-
EVMS Sites for Subjects with Fewer Than 5 PMS per HPF in the
Cervical Mucus after Sex | Ovaprene with at Least One PCT Cycle |
| 14.2.2.3-E           | Summary of Cervical Mucus pH Values at Study Site EVMS   | Ovaprene with at Least One PCT Cycle |

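### The ferrous gluconate level 'associated with success' is summarised in successful cycles with no failing-cycle comparison, so it cannot show a link with sperm, and reaching or keeping it would describe release only

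*SAP*

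**What the plan says.** Protocol 5.2 sets three linked release objectives: find the pre-sex FG levels that go with success (2a), find how long after insertion those levels are reached (2b), and find whether they are still there late in wear (2c). Success is an average of fewer than 5 PMS per high power field.

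- **Level.** Protocol 14.2.3: "The mean, median, SD, and IQR of ferrous gluconate values associated with fewer than 5 progressively motile sperm per HPF will be calculated". SAP 3.6, secondary c), summarises the same quantity by visit: "Levels of ferrous gluconate in CVF before sex that are associated with fewer than 5 progressively motile sperm per HPF".
- **All women.** Protocol 14.2.3 adds that the same statistics for "ferrous gluconate values at each time point at which it is collected will also be calculated across all women". These are not split by postcoital result.
- **Use of the level.** SAP 3.6, secondary d), says the safety-cycle data allow estimation of "how long after insertion it takes to reach the target concentration levels associated with success and whether target levels are still present". It gives no number and no rule for either judgement.
- **Tables.** SAP 4.2.1 pairs each all-subject FG table (14.2.2.1-E and -NE, 14.2.2.2-E and -NE) with a success-only version, for example "Summary of the Levels of Ferrous Gluconate in CVF at Study Site EVMS for Subjects with Fewer Than 5 PMS per HPF". None is listed for 5 or more PMS. The only graph in SAP 4.2.3 is of vaginal pH.
- **A fixed target.** SAP 3.6, secondary b): "Determine whether the minimum target level of 8.2" µg/mL is achieved. This covers only the first 4-6 hours after insertion, at one site.

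**The concern.** An association needs both outcomes. A summary restricted to successes describes FG in women whose test succeeded, for whatever reason.

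The documents give other routes to success. Of the mesh tested in vitro over 20 hours, Protocol 11.1 reports that "there was no evidence of sperm passage through the Ovaprene™ mesh". The Protocol introduction says released acid may thicken mucus, and Appendix 2 counts an Ovaprene cycle with thick mucus and few or no sperm in the cervix as a success, provided sperm are found in the vagina or cervix. Protocol 11.1 also reports that no participant in the earlier Ovaprene study had forward-moving sperm. If failures are rare again, the success-only summary is close to the midcycle FG distribution of all users.

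At stake is the meaning of three secondary objectives. The result of 2a becomes the yardstick for 2b and 2c. If it carries no information about sperm, a finding that the level is reached, or still present, says how the ring releases FG. It does not say that the amount released matters.

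**Working it through.** The plan has no power, error rate or threshold to reproduce; Protocol 14.1 says the size was not set statistically. The check asks what the planned outputs show when FG does and does not matter.

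**Inputs from the documents.** About 25 completers x 2 Ovaprene postcoital cycles = 50 cycles. Pre-sex FG is sampled at OP2 in each (Protocol 9.5.1). The last safety-cycle sample is at OS5.

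**Assumptions (not in the documents).** FG is lognormal with median 20 µg/mL and log SD 0.5 between and 0.4 within women, a total of √(0.5² + 0.4²) = 0.64. Success is 80, 90 or 95% per cycle at the median FG level. FG either has no effect or a strong one (log-odds of success rise by 2 per unit of log FG). There are 4,000 simulated trials per scenario.

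**Step 1. No effect.** If FG is independent of outcome, the distribution of FG given success equals the distribution of FG. Simulated medians are 20.2 (successes) and 20.2 (all cycles) at all three success rates. A level is still produced.

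**Step 2. What the two planned tables show under a strong effect.**

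| Success rate at median FG | All-cycle median | Success-only median | Ratio |
|---|---|---|---|
| 80% | 20.2 | 23.6 | 1.17 |
| 90% | 20.2 | 22.2 | 1.10 |
| 95% | 20.2 | 21.3 | 1.06 |

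The shift shrinks as failures become rare. In the limiting case where the lowest 5% of FG values are exactly the failures, the success-only median is the 52.5th percentile of all cycles. The ratio is exp(0.063 x log SD): 1.03 at log SD 0.5 and 1.06 at 1.0. Shifts of that size would be hard to see in tables split by site group and visit.

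**Step 3. Successes beside failures.** At 80%, the medians are 20.2 against 20.7 with no effect and 23.6 against 12.7 with the strong effect (where overall success is 74%). The contrast separates the two cases.

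**Step 4. How many failures there may be.** Expected failures = 50(1 - p); the chance of none = p^50, with cycles treated as independent.

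| Success rate p | Expected failures | Chance of none |
|---|---|---|
| 90% | 5 | 0.5% |
| 95% | 2.5 | 7.7% |
| 98% | 1 | 36% |

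Two-sided 5% power for a 1-SD difference in log FG is 28% with 2 failures, 39% with 3, 56% with 5 and 81% with 10.

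**Step 5. Is the level then automatically maintained?** With no FG effect, this is the share of trials in which the OS5 median is at or above a reference taken from the successful cycles. Both references are assumptions, since the SAP names none.

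| FG at OS5 relative to midcycle | Lower quartile | Median |
|---|---|---|
| unchanged | 99% | about 50% |
| 25% lower | 76-79% | 2-4% |
| 50% lower | about 5% | 0% |

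With total log SD from 0.5 to 1.0, half the variance between women, a 20% fall gives about 77-95% (lower quartile) and 4-19% (median). A 50% fall gives under 1% to about 44%, and under 1%. The answer depends on release and on the reference chosen.

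**The case against.** The strongest reply is that this is a descriptive feasibility study. The plan says 'associated with'; it claims neither causation nor a required level. Failing cycles are not discarded either. They are in the all-subject tables, and where the numbers match, the failing mean can be recovered as (N x mean for all - S x mean for successes) / (N - S), with N cycles and S successes. SAP 4.2.2 commits to listing all data, including vaginal samples, cervical mucus and the iron assay, so a reader could look up a handful of failures. The table shells are a separate document not available here. With few failures, an added comparison would have little power anyway.

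Much of this stands. A reader might infer that the planned outputs cannot tell a real link from none. The documents do not support that, because the information is recoverable in part. But the back-calculation does not give medians or IQRs. It also needs matching counts, and the success-only titles refer to subjects without saying how a woman with one success and one failure is counted. The listings hold FG and PMS separately. Even a modest claim of association needs the other outcome group. Low power is a reason to report the limit openly.

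**Conclusion.** The concern holds for the missing comparison. As written, the analysis yields a level for objective 2a whether or not FG affects sperm, and that level becomes the benchmark for 2b and 2c. Reaching or keeping it would describe release only and would not be evidence that FG acts on sperm.

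A reader might go further and infer that the level is bound to be found reached and maintained even with inert FG. The documents do not support that. They state no rule for either finding, and Protocol 11.1 describes burst, erosion and diffusion stages in vitro, so constant release cannot be presumed. In the working, the OS5 result ranges from 99% down to 0% according to the fall in FG and the reference used.

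The primary endpoint is unaffected. FG levels, variances, success rates and strength of effect are all assumed; the gap in the planned tables is not. This is a low-cost improvement to a secondary analysis.

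**What to change.** 1. In SAP 3.6 c) and the success-only tables, show OP2 FG by cycle for fewer than 5 PMS and for 5 or more PMS in adjacent columns.
2. List each failing cycle's OP2 FG, and plot OP2 FG against the average PMS count for all Ovaprene postcoital cycles.
3. Label the success column 'levels observed in successful cycles', and state that no success-associated level can be identified if there are no or very few failing cycles.
4. In SAP 3.6 d), state numerically which level is used for time to reach and persistence. Report the 8.2 µg/mL target alongside it, not in place of it: substitution would change objectives 2b and 2c in Protocol 5.2, and the SAP applies that figure only to the first hours at one site.
5. While editing d), reconcile the timing. Objective 2c refers to 27-29 days after insertion, whereas Protocol 9.4.1 places OS5 at 21-23 days after insertion, about cycle day 27-29.

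The cost is SAP wording, one column, one listing and one plot, from data already collected. The downside is that with few failures the report must say that the link between FG and success could not be assessed.

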# c) Visit OP3, the PCT visit, 2-3 hours after intercourse and within 27 hours of the CMC:

The participant will return to the clinic 2-3 hours after coitus ends and within 27 hours of the mucus check visit.

- Diary review, AEs, medications, and indications for a directed physical exam, wet mount, and other tests will be managed as described for Visit 2 (BP1)
- An acceptability questionnaire will be administered.
- The participant will undergo a pelvic exam:
  - o Signs of irritation of the external genitalia, cervix, and vagina, as observed with the naked eye, will be noted.
  - o The position of the device relative to the cervix will be noted.
  - o Cervical mucus will be examined for pH, ferrous gluconate, midcycle characteristics, and the presence of sperm (see **Appendix 2**).
  - o Vaginal sample(s) will be collected for pH, ferrous gluconate, and the presence of sperm.
  - o At sites other than EVMS, vaginal samples will be collected for antibacterial activity and soluble markers.
  - Results of the test PCT will be interpreted as shown in Appendix 3. A successful test PCT will show mucus containing an average of <5 progressively motile sperm per HPF.
- At the EVMS site only:
  - o At 0.5, 1, 2, 4, and 6 hours after the PCT: u
    - Vaginal sample(s) will be collected for pH and ferrous gluconate.
  - o At 6 hours after the PCT, if possible:

<sup>t "Other vaginal activity" includes insertion of vaginal medications/products other than the study product (prescription or over-the-counter), as well as insertion of sex toys, fingers, or anything else into the vagina. Tampons may be used during all days of menses in the Baseline PCT and Caya PCT cycles, but only during the first three days of menses in Ovaprene cycles.

<sup>u Samples will be collected at as many of these timepoints as possible.

Version: 06.00 (FINAL) Date: June 13, 2019

- Vaginal sample(s) for antibacterial activity and soluble markers will be collected.
- The participant will be instructed to refrain from intercourse and other vaginal activity until after Visit OP4, 24 hours after Visit OP3.

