#### 3.1.3 Analysis Conventions

This section details general policies used for the statistical analyses. Departures from these general policies may be given in the specific detailed sections of this statistical analysis plan. When this situation occurs, the rules set forth in the specific section take precedence over the general policies. The following policies will be applied to all data presentations and analyses.

- Discrete variables' summary statistics will consist of the number and percent of responses in each category
- Continuous variables' summary statistics will include the sample size (number of non-missing observations), mean, median, standard deviation (SD), minimum and maximum, abbreviated as "6-number summary statistics", where minimum and maximum may be replaced with 25th and 75th percentiles, i.e., interquartile range (IQR), if desired.
- All mean values will be formatted to one more decimal place than the measured value. Standard deviation values will be formatted to two more decimal places than the measured value. Median values will be formatted to same decimal place as the measured values when that is possible without losing accuracy; otherwise, they will be formatted to one more decimal place than the measured values.
- All percentages will be rounded to one decimal place. The number and percent of responses
  will be presented in the form XX (XX.X), where the percentage is in the parentheses. The
  decimal of the percentage may be dropped due to space constraints when creating a table.
  The denominator for percentage calculations will be the number of non-missing observations,
  or the analysis population's sample size if no such number of non-missing observations is
  presented along with the categorical values.
- All by-subject data listings will be sorted for presentation in order of site number, subject number, and date of procedure or event.
- When necessary for analysis purposes, partial dates will be completed (i.e., turned into complete dates) using the most conservative approach: for example, if a concomitant medication start date had Month and Year parts only, it's assumed to be the first day of that month; while if the stop date had Month and Year parts only, it's assumed to be the last day of that month.
- All analysis and summary tables will have the population sample size in the column heading.
- Calculating change from Baseline to a visit will be done as follows:

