#### 3.6 Efficacy Analysis

All efficacy analyses will be done for the Ovaprene with at Least One PCT Cycle population, and may be repeated for Treated with Caya population when necessary. The primary efficacy analysis will be the changes in PCT results due to Ovaprene® device use, and consists of the following 6 endpoints:

a) The proportion (and 95% exact binomial confidence interval ) of subjects with an average of fewer than 5 progressively motile sperm per HPF in cervical mucus, after sex at ovulation in the absence of the device. This needs to use the "Average number of progressively motile sperm" (SAS variable name MUAVPMS) in Cervical Mucus CRF, and count the number of subjects with MUAVPMS < 5.0 at the Visit 3 (BP2); then divided by the total number of subjects with PMS measurements at this visit, and finally converted to a percentage (multiplied by 100). In the data listing of PMS data, the data that occur in a cycle after a dislodgement in the e-diary, and clinician noted dislodgement, will be flagged.

This primary efficacy analysis will be repeated by subgroups for:

- (1) Had vaginal ring use before enrolling in the study vs. Never had
- (2) Had vaginal delivery vs. caesarean birth
- (3) BMI ≥30 (Obese) vs. <30 at Baseline
- (4) Study site EVMS vs. Non-EVMS study sites
- (5) Device position at the time PCT: Over cervical os, Not over cervical os on anterior vaginal wall, Not over cervical os and not on anterior vaginal wall

- (6) Dislodgments (dislodgement reported in cycle before the PCT visit vs. no dislodgements reported in cycle before PCT).
- b) The sample size, mean, median, standard deviation, and interquartile range (IQR, i.e., 25th and 75th percentiles), for the average number (across 9 HPFs) of progressively motile sperm per HPF in cervical mucus, across all treated subjects, in the absence of the device. This is to summarize the same field (MUAVPMS) in the above Bullet a) as a continuous variable at Visit BP2.
- c) The proportion of subjects (and 95% exact binomial confidence interval) with an average of fewer than 5 progressively motile sperm per HPF in cervical mucus, in the presence of the Ovaprene® device. This is similar to that in Bullet a), but will be done at Visit OP3A, and at Visit OP3B, by sub-setting the CRF data at VISIT\_ID = 14, and at VISIT\_ID = 19, respectively.

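### Ferrous gluconate before and after sex is summarised one time point at a time; the within-woman change with a 95% CI should be added, as the SAP already plans a difference for pH

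*SAP*

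**What the plan says.** Protocol 5.2, objective 2 d), asks what FG levels are after sex at ovulation and, if they differ from before, how long they take to come back. Protocol 4 (release question 4) and endpoint 2 c) in Protocol 6 and SAP 2.4 repeat this. SAP 3.6, secondary item e), says the data will allow "determination of whether they are different from before sex and, if so, how much time is needed to return to pre-sex levels".

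The analysis offered for e) is in the same terms as item d): "Summary statistics of sample size, mean, median, standard deviation, and IQR will be presented by visit and assessment timepoint". Protocol 14.2.3 plans the same kind of output: "mean, median, SD, and IQR of ferrous gluconate values at each time point at which it is collected will also be calculated across all women". Tables 14.2.2.1-E and 14.2.2.1-NE are titled as summaries of levels, and the only planned graph (SAP 4.2.3) is of pH.

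For pH, SAP 3.6 f) goes further: "Six-number summary for the observed values and difference between pre-sex and after sex will be presented by visit".

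Protocol 9.5.1 collects vaginal FG at OP2 (before sex), OP3 (2-3 hours after sex) and OP4 (24 hours after the PCT) at all sites. EVMS adds samples at 0.5, 1, 2, 4 and 6 hours after the PCT, with the footnote "Samples will be collected at as many of these timepoints as possible".

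**The concern.** The question is about change within a woman, and the planned output describes each time point by itself. A reader of the tables has to put the OP2 row beside a later row and judge by eye whether FG moved or came back. Two things make that unreliable. The rows may not contain the same women. And the spread shown in each row is spread between women, which does not show how precisely the change is known.

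What is at stake is how far objective 2 d) can be answered. If two rows look alike, the report cannot separate good evidence of little change from too little information. If they look different, it cannot separate a change from a difference in who was sampled.

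**Working it through.** The plan gives no sample size, SD, interval or margin for this endpoint, so there is no figure to reproduce.

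**1. What is planned for comparable measures.** A change or difference is specified for sperm counts (SAP 3.6, primary e), laboratory values (3.7.2), Nugent score, antibacterial activity and soluble markers (3.7.6), and pH (3.6, secondary f). FG in secondary e) has none. The "95% exact binomial confidence interval" in SAP 3.6 is for the sperm-count proportions only. The general rule in SAP 3.1.3, "Calculating change from Baseline to a visit will be done as follows", does not name OP2 as the FG baseline.

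**2. Who is in each row.** Let A be the women with an OP2 value and B those among them who also have a value at time t. Then

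mean of post in B − mean of pre in A = mean of (post − pre) in B + [mean of pre in B − mean of pre in A].

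The first term on the right is the quantity wanted. The bracket reflects only who was sampled. It is zero if no time point is missed, and restricting to women with both values removes it.

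**3. Precision.** With SD s at both times and within-woman correlation r, the standard error of the mean change is s × √(2(1−r)/n). Treating the rows as unrelated gives s × √(2/n). The ratio of the two is √(1−r): 0.84, 0.71 and 0.55 for r = 0.3, 0.5 and 0.7. The separate rows show s and n but not r.

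The 95% interval for the post/pre ratio is the estimate times or divided by exp(t × SE), with t on n−1 degrees of freedom when paired and 2n−2 when not. The inputs are assumptions: log-SD 0.5 or 1.0, r = 0.3 or 0.7, and 5, 8 or 12 EVMS women. The protocol synopsis gives 3-5 centers and about 25 completers, but no number for EVMS.

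Example, n = 8, log-SD 0.5, r = 0.7: SD of the difference = 0.5 × √0.6 = 0.387; SE = 0.387/√8 = 0.137; t = 2.365; exp(0.324) = 1.38.

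| n | log-SD | paired, r = 0.3 | paired, r = 0.7 | rows treated as unrelated |
|---|---|---|---|---|
| 5 | 0.5 | 2.08 | 1.62 | 2.07 |
| 5 | 1.0 | 4.35 | 2.62 | 4.30 |
| 8 | 0.5 | 1.64 | 1.38 | 1.71 |
| 8 | 1.0 | 2.69 | 1.91 | 2.92 |
| 12 | 0.5 | 1.46 | 1.28 | 1.53 |
| 12 | 1.0 | 2.12 | 1.64 | 2.33 |

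Across any line, the planned rows look the same while the true precision of the change differs. At n = 5 and r = 0.3, pairing gains nothing in width.

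**4. Overlap of rows.** In 20,000 simulated trials per setting with the same log-SDs and correlations and a true ratio of 0.70, the two IQRs overlapped in 77-96% of runs at n = 8. The model is symmetric on the log scale, so the same holds for a rise of the same factor (1/0.70 = 1.43). The medians do better: they were in the wrong order in 3-24% of runs.

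**The case against.** The strongest reply is that this is a descriptive feasibility study. Its size was not set on statistical grounds, the endpoint itself is a set of levels, and the remark about what the data allow is a rationale. No test, margin or rule for declaring return is written, so no false conclusion is planned. That stands. A reader might infer that the plan will declare FG unchanged or recovered because rows overlap, but neither document says so.

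A reader might also infer that FG falls after sex and that contraceptive action is then at risk. The documents give no direction. For contraceptive action, SAP 3.6 c) and d) look at levels associated with a successful PCT, not at return to a woman's own earlier value.

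Third, a reader might infer that a formal margin is needed before return can be claimed. The documents supply none for this purpose. With 0.80 purely as an illustration, a rule on the lower 95% limit would confirm a true return in only 7-29% of runs at n = 8 under the assumptions above. Such a rule would usually be inconclusive and is not recommended here.

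The single-site point is partly met already. The FG tables are split into EVMS and non-EVMS, so hourly EVMS rows sit beside EVMS OP2 rows, and only missed time points change who is compared. Sample size is shown in each row, and individual values will be listed. The table shells are a separate document not available here. None of this supplies a planned paired summary.

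**Conclusion.** The point holds as a minor, free improvement to a descriptive secondary endpoint. The SAP states a pre/post purpose for FG and plans no pre/post quantity for it, while planning one for pH in the next item.

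Missed hourly samples can put different women in different rows, and separate SDs and IQRs do not give the precision of the change. The size of the effect cannot be fixed from the documents. On the assumed inputs, the interval factor at n = 8 runs from 1.38 to 2.69, and rows with the same SD and n do not show which of the two correlations applies. The conclusion that a paired summary is needed does not depend on those inputs. It follows from the question asked and from the pairs already being collected.

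**What to change.** In SAP 3.6 e), and in Tables 14.2.2.1-E and 14.2.2.1-NE, add the within-woman change, or log ratio, in vaginal FG from OP2 to OP3 and to OP4. In the EVMS table, add it to each of the 0.5, 1, 2, 4 and 6 hour samples as well. Report it separately for the two Ovaprene PCT cycles, in women with both values, with the number of pairs and a 95% CI. Name OP2 as the pre-sex reference.

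Describe time to return from these paired estimates and intervals, and add one sentence that overlap of separate summaries will not by itself be reported as no difference or as return. Cervical-mucus FG is called exploratory in the protocol and is not collected at the hourly points or OP4, so there only the OP2 to OP3 change is available.

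The cost is a few lines of SAP text and some added table rows, with no new samples or visits. If the log ratio is chosen, a line on values below the assay limit is needed. With few EVMS women the intervals will be wide, and the report should show them as they are.
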